2.2 Study Design

The study is designed as a randomized controlled trial. Primary outcome was the evaluation of %EWL between 2 groups. Secondary outcomes were evaluation of morbidity, mortality, incidence of reflux symptoms and Quality of Life score between the Groups.From January 2015 to November 2017, a series of 218 consecutive patients suffering from morbid obesity and scheduled for LSG were included; informed consent was obtained from each participant before surgery.

Inclusion criteria were morbid obesity defined as BMI 40 kg/m² and age between 25–50 years old. Obesity-related comorbidities included Type 2 Mellitus Diabetes (T2MD), hypertension, hyperlipidemia, bronchial asthma, osteoarthritis and degenerative joint disease.

Exclusion criteria

Patients with previous bariatric surgical procedures, endocrine disorders causing obesity (as hypothyroidism and Cushing disease), pregnancy or lactation, psychiatric illness, or recent diagnosis of malignancy, inflammatory bowel disease, Barrett's esophagus, and GERD with esophagitis scored as or greater than grade B, a large hiatal hernia (>3 cm) were excluded from the study. In case of absence or grade A esophagitis, GERD was also considered as severe with GERD-HRQL > 30 and when interfering with daily activities or inducing dietary restriction despite, also these were excluded.

One hundred-fifty patients were considered eligible and randomized in two Group (Group A n = 75, Group B n=75). All patients underwent elective laparoscopic LSG. In the case of conversion to open surgery, patients were excluded. Details of enrollment procedure are shown in Fig. 1.

Randomization

Participants were randomly assigned to one of the two groups using computer-generated permuted blocks (www.randomization.com). Outpatient clinic controls were done by surgeons/surgical residents/GP blinded for the groups. Patients were randomized into 2 groups based on the distance to pylorus of resection: Group A (n=75) at 2 cm, Group B(n=75) at 6 cm. Results were obtained at 1 and 2 years follow-up. The randomization scheme was generated using the web site Randomization.com (<http://www.randomization.com>).

Blinding Process

Patients, care providers, staff collecting data, and those assessing the endpoints were all blinded to treatment allocation. Patients were blinded to the surgical procedure performed until the final assessment of the study endpoints. Because the blinding of the operating surgeons was not feasible, they were not involved in the data collection and outcome assessment. Physicians in charge of patients' management were not involved in the operating room and were blinded to the surgical procedure. Data were collected and analyzed by physicians who were not involved in the patient's management during the whole RCT. For all patients enrolled in the study, a detailed letter of the protocol was sent to general practitioners, with a detailed calendar of clinical and/or instrumental follow-up data to be performed at the bariatric surgery center.

Study Protocol

Surgical Technique

The patient is placed in a split leg position with the surgeon located in between the patient's legs. Closed pneumoperitoneum was established using our standard technique of Veres needle insufflation in Palmer site and optical insertion of a 12-mm port at a supraumbilical site (10-15 cm from umbilicus) Two further 15-mm and 12-mm ports were placed respectively in the left and right ipocondrum as working ports. A subxiphoid track was created using a 5-mm port for placement of a liver retractor. CO₂ is insufflated up to 15 mmHg. In patients with higher body mass index who have severe visceral obesity, additional trocars can be added for retraction of the omentum or big fatty livers, to optimize the exposure to reach the left crus. Once the left crus is reached, an optimal exposure of the hiatus is mandatory to find incidental hiatal hernias and a complete dissection of the left crus performed to prevent retained fundus. The greater omentum was opened close to the stomach wall in some part in between the fundus and the antrum to have greater curvature completely detached from the stomach; this dissection starts at 2 cm proximal to the pylorus and continued along the greater curvature to the left crus in Group A with Blunt Tip (Medtronic Inc., Dublin, Ireland), and at 6 cm proximal to the pylorus in Group B. Posterior adhesions if present, were carefully divided. The left gastrophrenic ligament was divided to expose the angle of His to identify the complete hiatus and fundus. A bougie was positioned before starting resection of the stomach. We use a 36Fr bougie The starting point from the pylorus to begin the gastrectomy was 2 cm in Group A and 6 cm in Group B. To perform gastrectomy, we used a Medtronic Tri-Staple® SIGNA (Medtronic Inc., Dublin, Ireland) with GORE® SEAMGUARD® Bioabsorbable Staple Line Reinforcement. we have chosen cartridges Black at the antrum level and finished with a purple cartridge. We always checked the posterior wall before firing. Once we have reached the proximal stomach, the stapler has to be positioned 1 cm lateral to the left of the angle of His to avoid inclusion of esophageal tissue. Methylene blue test is performed routinely.

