Study Protocol

“Does Antrum Size Matter in Sleeve Gastrectomy?”

Study Protocol

“Does Antrum Size Matter in Sleeve Gastrectomy? ”

BACKGROUND

Laparoscopic sleeve gastrectomy (LSG) is currently the most frequent primary bariatric procedure performed worldwide. LSG is safe and effective in terms of excess weight loss. It is a powerful metabolic operation that activates significant hormonal pathways that lead to changes in eating behavior, glycemic control and intestinal functions. LSG can be a faster procedure for its technical aspects (any need for intestinal anastomosis, being limited to the stomach transection). The most frequent and sometimes dangerous complications are leaking, hemorrhage, splenic injury, stenosis and Gastroesophageal Reflux Disease (GERD)(1). Despite its established efficacy and safety, dispute still exists on optimal operative technique for LSG: bougie size, distance of resection margin from the pylorus, the shape of section at the gastroesophageal junction, staple line reinforcement and intraoperative leak testing are among the most controversial issues (2). Indeed, different Authors have adopted a resection distance from the pylorus between 2 and 6–7 cm with various reasons (3). In favor of resections more distant to the pylorus, Authors argue that it seems to improve gastric emptying, prevent distal stenosis and reduce intraluminal pressure, potentially leading to a lower incidence of fistula and/or reflux. On the other hand, resections close to the pylorus seems to reduce more the gastric distensibility and increase intragastric pressure, potentially leading to a better satiation with less oral intake (4, 5). However, only few studies have investigated the differences between these two approaches (3). Thus, the primary aim of this randomized monocentric study is to evaluate variations in percentage of excess weight loss (%EWL) at 1 and 2 years follow-up after LSG in subject with a gastric resection starting from 2 cm from the pylorus (wide antrectomy) compared to those with a gastric resection starting from 6 cm from the pylorus (small antrectomy). Secondary aim-points are represented by evaluation of differences in morbidity, mortality, tolerance to food, incidence of reflux symptoms and GERD Health-Related Quality-of-Life (GERD-HRQL) score between the two groups.

Material and Methods

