2.5 Post-operative evaluation

All patients were actively clinical followed up regularly at 3, 6, 12 and 24, included GERD-HRQL. UE was performed in all patients at 12 or 24 months. Significant vomiting and food intolerance were evaluated at 6, 12 and 24 months follow-up. Vomiting was considered significant when occurring at least three times a week and food intolerance was defined as vomiting occurring almost each day. Esophageal biopsies were performed only in case of esophagitis \geq B (9).

Weight loss parameters were recorded at 3, 6, 12 and 24 months after the LSG : BMI (in kg/m²), %EWL and percentage total weight loss %TWL from baseline. The secondary endpoints were GERD and esophagitis studied with Upper endoscopy and GERD score

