2.6 Statistical Analysis

Statistical analysis was performed using Graphpad Quick Calcs (GraphPad version 6.04 for Windows, GraphPad Software, La Jolla California USA). Baseline comparisons were performed using chi-square tests and T-tests. Continuous variables are expressed as mean \pm standard deviation (SD). Differences between preoperative and postoperative parameters were compared by Wilcoxon paired rank test. For all tests, a two-sided $p < 0.05$ was considered statistically significant.

Sample size

THIS IS A CONTROLLED RANDOMIZED STUDY OF BINARY NON-INFERIORITY OUTCOME IN PARALLEL GROUPS. IF THERE IS TRULY NO DIFFERENCE BETWEEN THE STANDARD AND EXPERIMENTAL TREATMENT, THEN 138 PATIENTS ARE REQUIRED TO BE 90% SURE THAT THE LOWER LIMIT OF A ONE-SIDED 95% CONFIDENCE INTERVAL (OR EQUIVALENTLY A 90% TWO-SIDED CONFIDENCE INTERVAL) WILL BE ABOVE THE NON-INFERIORITY LIMIT OF -10. SAMPLE SIZE WAS CALCULATED WITH SEALED ENVELOPE LTD. 2012.

Appendix 2

Chief Investigator: [name], PhD – UOC Chirurgia Generale – Ospedale A. Rizzoli –

Lacco ameno napoli. [contact]; cellulare: [name].

Results summarized in the table:

Table 1 :Preoperative demographics data

Table 2: Weight, Body mass index, and the percentage of excess body weight loss and the Percentage Total Weight loss of the two groups at follow-up 3-6-12-24-months

Table 3: GERD Health-Related Quality-of-Life (GERD-HRQL) Score preoperative and postoperative scores follow-up 3-6-12-24 months

Table 4: Endoscopy Preoperative and at 1 and 2 years follow-up into two Groups

Table 1 Preoperative demographics data

Patients	Total	Group A (n=75)	Group B(n=75)
Age	33.6 ± 14	32.2 ± 8	34.2 ± 9
Male	39%	35%	38%
Female	61%	63%	62%
Height	151.2 ± 22	150.1 ± 23	152.8 ± 33
Weight kg	121.9 ± 21.7	124.5 ± 26.7	125.3 ± 23.5
BMI	44.23 ± 6.32	43 ± 8 (40–57)	44 ± 4(40–55)
ASA(I-II)(%)	65%	64%	66%
ASA(III-IV)(%)	35%	36%	34%
T2MD(%)	12(8.%)	7(9.3%)	5(6.6%)
Chronic obstructive pulmonary disease(%)	7(4.6%)	2(2.6%)	3(4%)
Heart Ischemia	1	0	0
Hypertension(%)	95(63%)	55(73.3%)	40(53.4%)

BMI body mass index, %EWL percentage excess weight loss, %TWL percentage total weight loss, Type 2 Mellitus Diabetes (T2MD)

Table 2: Weight, Body mass index, and the percentage of excess body weight loss and the Percentage Total Weight loss of the two groups at follow-up

Patients	3 months follow-up		p	6 months follow-up		p	12 months follow-up		p	24 months follow-up		p
	145/150			141/150			136/150			131/150		

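### Section 2.6 plans no baseline-BMI adjustment for %EWL, although %EWL depends arithmetically on starting BMI; the possible shift is small but comparable with the reported gaps, and its size and direction are provisional

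*Combined protocol and SAP*

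**What the plan says.** The Background gives the primary aim as "variations in percentage of excess weight loss (%EWL) at 1 and 2 years follow-up after LSG", and section 2.2 repeats it: "Primary outcome was the evaluation of %EWL between 2 groups". No formula for %EWL and no reference (ideal) weight is given.

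Section 2.5 says that the weight measures recorded at 3, 6, 12 and 24 months include "EWL and percentage total weight loss %TWL from baseline". The title of Table 2 announces "Weight, Body mass index, and the percentage of excess body weight loss and the Percentage Total Weight loss of the two groups at follow-up". In the text available, that table shows only BMI and EBWL% rows.

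On analysis, section 2.6 says "Baseline comparisons were performed using chi-square tests and T-tests" and "Differences between preoperative and postoperative parameters were compared by Wilcoxon paired rank test", with a two-sided 5% level for all tests. It names no between-arm test for %EWL and no covariate-adjusted analysis. BMI is part of the preoperative evaluation and is summarised in Table 1 for 75 patients per arm.

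**The concern.** %EWL divides the weight lost by the weight above an ideal. Two patients who lose the same fraction of body weight therefore get different %EWL values if they start at different BMIs, and the lighter one scores higher. A comparison of raw %EWL carries any baseline BMI difference between the arms straight into the primary result.

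The printed baseline means differ by one BMI unit, with Group A lower. The reported %EWL gaps are small, so even a shift of one or two points could change how they are read. Adjustment for baseline BMI would remove most of this dependence using data already held, and the plan does not include it.

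**Working it through.** **Inputs.** Table 1: baseline BMI 43 ± 8 (range 40–57) in Group A, 44 ± 4 (40–55) in Group B, 44.23 in total; weight 124.5 and 125.3 kg (total 121.9); height 150.1 and 152.8 cm. Table 2: %EWL 63.7 ± 14.1 (n=67) against 59.6 ± 12.5 (n=69) at 12 months, and 62.8 ± 13.1 (n=65) against 61.6 ± 10.5 (n=66) at 24 months; BMI 24.2 against 27.5, and 25.2 against 26.2. Assumed, because not stated: ideal BMI 22 to 25.

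**1. The printed comparisons, unadjusted.**
- 12 months: difference 63.7 − 59.6 = 4.1; SE = √(14.1²/67 + 12.5²/69) = 2.29; two-sided t-test p = 0.075; 95% CI −0.4 to 8.6. The printed P<0.05 is not reproduced.
- 24 months: difference 1.2; SE = √(13.1²/65 + 10.5²/66) = 2.08; p = 0.56; 95% CI −2.9 to 5.3. This agrees with the printed p>0.05.

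**2. Shift from the baseline gap alone.** %EWL = %TWL × BMI₀/(BMI₀ − ideal). Set Group A at 60% EWL with BMI 43, and give Group B the same %TWL with BMI 44.
- Ideal 25: %TWL = 60 × 18/43 = 25.1; Group B's %EWL = 25.1 × 44/19 = 58.2; shift 1.8.
- Ideal 22: %TWL = 60 × 21/43 = 29.3; Group B's %EWL = 29.3 × 44/22 = 58.6; shift 1.4.
- As a share of the 12-month gap: 1.4/4.1 = 34% to 1.84/4.1 = 45%. Both values exceed the 24-month gap of 1.2.
- Starting from the printed 63.7 instead of 60 scales the shift by 63.7/60, to about 1.5 to 1.95.

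**3. Rounding of 43 and 44.** True means of 42.5 and 44.49 give a shift of 2.8 (ideal 22) to 3.6 (ideal 25). True means of 43.49 and 43.5 give about 0. The range is 0 to 3.6 points.

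**4. Is 43 against 44 dependable?**
- With equal arms the total mean must lie midway between the arm means. Even at the rounding limits that is at most (43.49 + 44.49)/2 = 43.99, below the printed 44.23. Total weight, 121.9 kg, is below both arm means.
- Mean 43 with range 40–57 allows an SD of at most √(3 × 14 × 75/74) = 6.5 (7.5 at the extremes of rounding), not 8.
- Mean weight over squared mean height gives 124.5/1.501² = 55.3 (A) and 125.3/1.528² = 53.7 (B). This is only indicative, since a ratio of means is not a mean BMI, but it reverses the direction. With ideal 25 the factors are 1.826 and 1.872, so the shift is 60 × (1.872/1.826 − 1) = about 1.5 points in Group B's favour.

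**5. Do the Table 2 rows agree with each other?** From the BMI rows and baselines of 43 and 44:
- 12 months: %TWL = 18.8/43 = 43.7 (A) and 16.5/44 = 37.5 (B), gap 6.2 (4.9 to 7.6 over the rounding of the baselines).
- 24 months: 17.8/43 = 41.4 (A) and 17.8/44 = 40.5 (B), gap 0.9 (−0.4 to 2.3).
- The same rows imply %EWL (ideal 25) of 18.8/18 = 104 and 16.5/19 = 87 at 12 months, and 99 and 94 at 24 months, far from the printed values. Baseline means cover all 75 per arm and follow-up means only those seen, but no more than 10 patients per arm are missing.

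**6. Is the baseline gap more than chance?** SE = √(8²/75 + 4²/75) = 1.03; p = 0.33. With Group A's SD set to 6.5, the SE is √((6.5² + 4²)/75) = 0.88 and the gap is still only about 1.1 SE.

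**The case against.** The strongest reply is that the size of the shift rests on inputs that the documents themselves undermine. It assumes equal %TWL of 25–29% in the two arms, yet the BMI rows of Table 2 imply about 44% against 38% at 12 months. On that scale, which uses no ideal weight, the 12-month gap does not shrink. The reference weight is undefined, the baseline means are whole numbers, and Table 1's weight and height point the other way. All of this stands, and it rules out any firm figure.

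It is also fair that a one-unit gap between randomised arms is compatible with chance. A reader might infer a bias built in for Group A; the documents do not support that. But adjusting for a baseline variable that enters the outcome's own formula does not depend on showing an imbalance.

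Two further inferences should be resisted. One is that the sponsor withheld %TWL: the measure is recorded and announced, and its row (like the weight row) may have been lost when the table was read from PDF. The other is that the printed 12-month P<0.05 is simply wrong. No between-arm test is named, and a rank test on patient data could differ. A one-sided t-test would give 0.075/2 = 0.037, but section 2.6 specifies two-sided tests.

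**Conclusion.** The point holds as a gap in the analysis plan. The primary measure depends on starting BMI, baseline BMI is collected, and section 2.6 plans no adjusted between-arm comparison. On the printed means, with ideal BMI 22–25 and equal %TWL, the imbalance could move the %EWL difference by about 1.4 to 1.8 points (0 to 3.6 with rounding), against gaps of 4.1 and 1.2.

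A reader might go further and conclude that part of the 12-month gap and all of the 24-month gap are artefact. The documents do not support that. The BMI rows still favour Group A in relative weight loss, by about 6 points at 12 months and 1 at 24 months (the latter of unsettled sign once rounding is allowed for). Those rows in turn conflict with the %EWL row. Calling the 24-month gap an artefact would also change nothing, since it is already reported as non-significant. The practical weight falls on 12 months, where the unadjusted p of about 0.075 leaves little room for an unadjusted, baseline-dependent measure.

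**What to change.** In section 2.6, estimate the between-arm %EWL difference at 12 and 24 months with a linear model adjusted for patient-level baseline BMI, and report it with a 95% CI. Because results are already in the document, mark this analysis as added and show the unadjusted difference beside it. State the formula and reference weight used for %EWL. Confirm that the announced weight and %TWL rows exist in Table 2, or add them, with the arm difference in %TWL and its 95% CI. Reconcile the BMI, weight, height and %EWL figures in Tables 1 and 2 before claiming a weight-loss difference.

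The cost is a sentence or two in section 2.6, at most two table rows and a check of the source data; nothing new has to be collected. The 12-month %EWL difference may shrink or grow as a result.

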This study was conducted from January 2015 to November 2017 in the Department of General and Emergency Surgery of "A. Rizzoli" Hospital in Lacco Ameno (Naples, Italy). All the procedures were

performed by the same surgeon. Morbid obesity was preoperatively diagnosed according to the International Federation for Surgery of Obesity (IFSO) guidelines (1). Patients were randomized into 2 groups: Group A (dissection starts at 2 cm proximally to the pylorus and continued along the greater curvature to the left crus) and Group B (dissection starts at 6 cm proximally to the pylorus and continued along the greater curvature to the left crus). Results were obtained at 1 and 2 years follow-up.

Pre-operative evaluation

Preoperative evaluation included anthropometric measurements (height in cm, weight in kg, Body Mass Index(BMI) in kg/m²), comorbidity evaluation [Glycated Hemoglobin(A1c), C-peptide, stimulated C-peptide, Electrocardiography (ECG), echocardiography, lower limbs US color-doppler study, thyroid function profile]. All patients were evaluated for the presence/absence of GERD before surgery. All patients were surveyed about the presence of heartburn and/or regurgitation with a specific questionnaire GERD HRQL questionnaire (6). Each of the 10 questions were rated from 0 (absence of symptoms) to 5 (severe symptoms) for a total score that may range from 0 to 50. Symptoms were defined as absent when patients reported a GERD-HRQL score of 0, mild from 1 to 15, moderate from 16 to 24, and severe from 25 to 50. Patients with GERD-HRQL score >16 was considered positive for GERD;(7). Atypical symptoms were also recorded. All patients underwent upper endoscopy (UE) after 20 days proton pump inhibitors (PPIs) or H2 blockers off, with Helicobacter Pylori(HP) test. When present, HP was eradicated according to Maastricht consensus(8). At UE, esophagitis presence was graded according Los Angeles Classification (9). PPI assumption and symptoms relief was also measured. In case of atypical symptoms and PPI refractoriness, pH-monitoring was indicated to confirm or exclude GERD diagnosis.

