	Group A (n=72)	Group B(n=73)	p>0.05	Group A(n=70)	Group B(n=71)	P<0.05	Group A(n=67)	Group B(n=69)	p	Group A(n=65)	Group B(n=66)	p>0.05
BMI	30.9 ± 5.32	34.7 ± 4.18	P<0.05	26.13 ± 7.32	31.06 ± 3.12	P<0.05	24.2 ± 3.4	27.5 ± 4.3	P<0.05	25.2 ± 4.4	26.2 ± 3.3	p>0.05
EBWL%	40.9 ± 8.1	31.60 ± 8.7	P<0.05	54.1 ± 11.3	48.20 ± 12.5	P<0.05	63.7 ± 14.1	59.6 ± 12.5	P<0.05	62.8 ± 13.1	61.6 ± 10.5	p>0.05

Results

Table 3 GERD Health-Related Quality-of-Life (GERD-HRQL) Score preoperative and postoperative scores

Patients	Preoperative 150/150		3 months follow-up 145/150		p >0.05	6 months follow-up 141/150		P <0.05	12 months follow-up 136/150		P <0.05	24 months follow-up 131/150		p >0.05
	Group A (n=75)	Group B (n=75)	Group A (n=72)	Group B (n=73)		Group A (n=70)	Group B (n=71)		Group A (n=67)	Group B (n=69)		Group A (n=65)	Group B (n=66)	
GERD HRQL Score<15			38(52.7%)	57(78%)	P <0.05	36(51.4%)	56(78.8%)	P <0.05	47(70.4%)	55(79.7%)	P <0.05	49(75.3%)	55(83.3%)	P <0.05
GERD HRQL Score >16<30	7(9.3%)	9(12%)	29(40%)	15(20.5%)	P <0.05	30(42.8%)	14(19.7%)	P <0.05	16(23.8%)	13(18.8%)	P >0.05	14(21.5%)	10(15.1%)	P >0.05
GERD HRQL Score >31	-	-	5(6.9%)	1(1.3%)	P <0.05	4(5.7%)	1(1.4%)	P <0.05	4(5.9%)	1(1.4%)	P <0.05	1(1.5%)	0	P <0.05
Significant Vomit	-	-	11(15,3%)	3(4.1%)	P <0.05	6(8.6%)	2(2.8%)	P <0.05	6(8.9%)	2(2.9%)	P <0.05	2(3.1%)	1(1.5%)	P <0.05
Intolerance to food	-	-	2(2.7%)	0	P <0.05	1(1.4%)	0	p >0.05	0	0	p >0.05	0	0	p >0.05

Table 4: Endoscopy Preoperative and at 1 and 2 years follow-up into two Groups

	Preoperative Patients 150		1 year follow-up Patients 108/150(72%)		2 years follow-up Patients 105/150(70%)	
	Group A 75	Group B 75	Group A 53	Group B 55	Group A 52	Group B 53
Esophagitis						
A	4(5.3%)	5(6.7%)	9(16.9%)	7(12.7%)	5(9.6%)	5(9.4%)
B	-	-	11(20.7%)	5(9%)	9(17.3%)	3(5.6%)
C	-	-	2(3.8%)	0	1(1.9%)	0
D	-	-				
Esophageal biopsy						
Metaplasia	-	-	0	0	0	0
Helicobacter Pylori	9(12%)	7(9.3%)				
Hiatal Hernia< 5 cm	1(1.3%)	2(2.7%)	-	-	-	-

Figure 1 Diagram of Patients eliability

Flow Diagram

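### Patients converted to open surgery are excluded, apparently after randomisation; any who exist should be analysed and counted in their assigned group

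*Combined protocol and SAP*

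**What the plan says.** Section 2.2 (Study Design) gives four statements in this order:

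- on allocation, "One hundred-fifty patients were considered eligible and randomized in two Group", with 75 in each group;
- on the operation received, "All patients underwent elective laparoscopic LSG";
- as the rule at issue here, "In the case of conversion to open surgery, patients were excluded";
- as the pointer to the flow diagram, "Details of enrollment procedure are shown in Fig. 1".

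The same section lists the outcomes other than %EWL: "Secondary outcomes were evaluation of morbidity, mortality, incidence of reflux symptoms and Quality of Life score between the Groups".

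Material and Methods says that all procedures were "performed by the same surgeon". The Blinding Process paragraph accepts that the operator knew the allocation: "Because the blinding of the operating surgeons was not feasible". Under Surgical Technique, the arms differ in where the resection starts, 2 cm or 6 cm from the pylorus, so the operation is itself the randomised treatment.

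Section 2.6 (Statistical Analysis) names no analysis set and has no rule for following or analysing converted patients. Table 3 is headed "Preoperative 150/150" at baseline, and Table 2 has 72 (A) and 73 (B) patients at 3 months. No reason is given for the shortfall.

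**The concern.** The other exclusion criteria can be settled before surgery. This one can be met only during surgery, once the surgeon is carrying out the allocated resection and knows which one it is. An exclusion made at that stage can depend on the arm. Blinded follow-up does not repair this, because the patient has left the comparison before follow-up starts.

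Two things are at stake. Randomisation protects the comparison of the groups as assigned, and dropping patients for an event during treatment weakens that protection. The rule also acts directly on two stated outcomes. Converted cases are likely to include difficult operations, and removing them can make morbidity and mortality look better, possibly more so in one arm. Tables 1 to 4 cover demographics, weight, reflux score with vomiting and food intolerance, and endoscopy. None reports operative complications or conversions, so a reader could not recover the excluded cases from them.

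**Working it through.** **Order of events.** Section 2.2 ties randomisation to eligibility, which rests on pre-operative criteria, and only then mentions surgery and conversion. The natural reading is that exclusion follows randomisation. This is an inference from sentence order. If patients were randomised in theatre, after the point at which conversion could occur, the rule would not be a post-randomisation exclusion.

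**How many patients could be involved.** The readable text gives no count of conversions. A conditional bound is possible if converted patients are among the 150 and were never followed. They must then be among those unseen at the first visit (Table 2):

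- Group A: 75 - 72 = 3
- Group B: 75 - 73 = 2
- Total: 5

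The larger shortfall at 24 months (150 - 131 = 19) does not widen this bound, since a patient excluded at surgery would already be missing at 3 months.

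**Difference in conversion rate, A minus B.** The extremes are:

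- all in A: 3/75 - 0 = +4.0 percentage points
- all in B: 0 - 2/75 = -2.7 percentage points

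If every such patient also had a complication (assumption), restoring them would move the morbidity difference by at most these amounts.

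**Effect on %EWL.** Suppose converted patients lie D points below their arm's mean. Restoring k of them to an arm of 75 moves that arm's mean by -(k/75) x D. The documents give no value for D, so a range is shown for the change in A minus B:

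| Assumed D | 3 in A only | 2 in B only |
|---|---|---|
| 10 | -0.40 | +0.27 |
| 20 | -0.80 | +0.53 |
| 40 | -1.60 | +1.07 |

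Using the 24-month attenders as the base changes little. For D = 20 the shifts are -3/(65 + 3) x 20 = -0.88 and +2/(66 + 2) x 20 = +0.59.

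**Scale.** From Table 2, A minus B is 63.7 - 59.6 = 4.1 at 12 months and 62.8 - 61.6 = 1.2 at 24 months. The 24-month standard error is sqrt(13.1²/65 + 10.5²/66) = 2.08. A shift of 0.80 is 0.80/2.08 = 0.38 of a standard error.

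**Numbers.** Losing 5 patients leaves 145, still above the 138 in the Sample size paragraph. The issue is bias and completeness of safety reporting, not power.

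**The case against.** The strongest reply is that the rule may never have been used. The sentence just before it says all patients had the laparoscopic operation, and the preoperative columns carry 75 and 75. Both favour few or no conversions. Fig. 1 is cited for enrolment and is missing here only because figures were not extracted, so the count may already be reported. Arm-dependent conversion is also not demonstrated: access, exposure, bougie and stapling are described alike for both arms. All of this stands, and it limits the point to the rule as written.

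Three stronger readings are tempting and unsupported:

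- A reader might infer that patients were removed and the results biased. No passage shows a single conversion.
- A reader might infer that 75/75 is a count after exclusion, which would leave the number removed without any bound. The text calls these the randomised patients, and nothing suggests otherwise.
- A reader might infer that a promised intention-to-treat analysis was broken. None is promised. The rule removes patients; it does not move them between arms.

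What the objection does not answer is that the rule, if applied, drops patients for an event during the allocated treatment, and that nothing elsewhere puts them back.

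**Conclusion.** The point holds as a flaw in the stated rule, with unknown and possibly zero realised effect. It rests on randomisation having preceded the operation, which the text implies but does not state.

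If converted patients are among the 5 unseen at 3 months, the effect on the A minus B difference in %EWL is small: about -0.8 to +0.5 points under an assumed 20-point deficit. The matching difference in conversion rate lies between -2.7 and +4.0 percentage points. For morbidity and mortality, where the rule acts most directly, the tables give no figures against which to judge this. The correction is worth making because it is cheap and settles the question either way.

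**What to change.** Replace the exclusion sentence with:

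> All randomised patients, including any converted to open surgery, are analysed in their assigned group using available follow-up, and are counted in morbidity and mortality; an analysis without conversions is reported as a sensitivity analysis.

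Alongside it:

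- Report the number of conversions by arm, in agreement with Fig. 1.
- State when randomisation took place relative to surgery.
- If converted patients were dropped and have no data, call the analysed set modified, not all randomised.
- If there were no conversions, say so; that closes the point.

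The cost is one sentence, one count per arm and one line on timing. No new data collection is needed. The downside is that converted patients may have little follow-up and may add slight variability to %EWL.
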